7.3 Data Analysis Plans

The feasibility of successful delivery of PRISMS will be measured using indicators such as recruitment and retention rates. Analysis of these primary indicators are described above.

Appropriate descriptive statistics will be calculated for other indicators of feasibility, quality of life; general, and physical, social/family, emotional, and functional subdomains, for participants and partners, by time point (T1, T2), and by group, and patient's health care services utilization (e.g., clinic visits, ER visits, and readmission) by group. This sample size (10 in each group) will ensure 80% power to detect a large effect size of 1.15 at the one-sided 0.05 significance level using a two-sample t-test to compare the difference in pre-post change (from T1 to T2), or mean level at T2 (if an outcome is only measured at T2), of a given outcome between the two intervention groups.

Appropriate exploratory analyses (e.g., trajectory analysis of frequently measured PRO outcomes), for the purpose of generating hypotheses, may be conducted.

All analyses will be conducted using an intention-to-treat approach, in which all randomized participants will be analyzed according to their assigned group, regardless of the extent of intervention actually received. Due to the fact that this is an exploratory proof-of-concept study, rather than a confirmatory study, we will not adjust for multiplicity when computing the CIs in conducting comparisons. Unless otherwise specified, all tests will be one-sided at an alpha level 0.05. All analyses will be conducted using SAS 9.4 (SAS Institute Inc., Cary, NC).

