4.5 Removal of Patients from Protocol

Participants can withdraw from study at any time.

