7.2 Sample Size and Accrual

We plan to recruit 20 patients with recent ostomy (within 4 weeks) and their caregiver (with a total of 20 patient-caregiver dyads and 40 individuals) and 3-5 health care providers. Based on previous experiences, we anticipate we will achieve data saturation among these participants. We claim such a study as

feasible if and only if both (i) recruitment rate (p) and (ii) retention rate (q) are large enough. More specifically, this is to test the following hypothesis: $H_0: p \leq 65\%$ or $q \leq 65\%$ vs $H_1: p \geq 80\%$ and $q \geq 80\%$. We will claim the study feasible (high recruitment rate and high retention rate) if we reach 29 or fewer patients/dyads to recruit 20 dyads, AND more than 14 (≥ 15 out of 20) participants remained in the study. This study reaches 76% power at alpha level 0.10. In addition, we will estimate the proportion and associated 95% confidence interval of patients' satisfaction with and perceived ease use of PRISMS. With 10 couples in the PRISMS arm and expected satisfaction rate of 70%, the width of the 95% CI will be around 0.58 (0.29 for 1-side width).

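### Section 7.3's 80% power for an effect of 1.15 assumes complete T2 data without saying so; at the 80% retention behind Section 7.2's own power it averages about 70%

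*Combined protocol and SAP*

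**What the plan says.** Section 7.3 gives the power for the between-group comparison: "This sample size (10 in each group) will ensure 80% power to detect a large effect size of 1.15". The test is a two-sample t-test at one-sided 0.05, used "to compare the difference in pre-post change (from T1 to T2), or mean level at T2" where an outcome is measured only at T2. The same section adopts intention-to-treat, under which "all randomized participants will be analyzed according to their assigned group, regardless of the extent of intervention actually received".

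Section 7.2 sets the number: "We plan to recruit 20 patients with recent ostomy (within 4 weeks) and their caregiver". It also makes retention one of two feasibility criteria. Feasibility is claimed "if we reach 29 or fewer patients/dyads to recruit 20 dyads", "AND more than 14 (≥ 15 out of 20) participants remained in the study". The null hypothesis puts recruitment or retention at 65% or below, and the alternative puts both at 80% or above. Section 7.2 then states: "This study reaches 76% power at alpha level 0.10".

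Section 4.5 says: "Participants can withdraw from study at any time". No section enlarges the sample for dropout or provides for replacing a dyad that leaves.

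**The concern.** Both forms of the tested outcome, change from T1 to T2 and level at T2, need a T2 value. The n in the power calculation is therefore the number with T2 data, and the calculation sets it equal to the number randomised. Next to it, Section 7.2 treats retention as an open question and calculates its own power with one participant in five lost. Two adjacent sections thus use different retention values, 80% and, without saying so, 100%. The second is worded as an assurance.

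What is at stake is how a non-significant between-group result would be read. Section 2.2 states directional hypotheses and Section 7.3 provides for one-sided tests. A reader who takes 80% power as assured would give such a result more weight than it can bear when this pilot is used to plan the definitive trial.

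**Working it through.** **Inputs.** From 7.3: 10 per group, standardised effect d = 1.15, one-sided alpha 0.05, two-sample t-test. From 7.2: retention q = 80% at the edge of the alternative, retention criterion 15 of 20, stated power 76%. The 90% retention figure below is my illustration, chosen because it lies inside 7.2's alternative.

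**Formula.** For n1 and n2 participants with T2 data, the degrees of freedom are n1 + n2 − 2 and the noncentrality is d × √(n1·n2/(n1 + n2)). Power is the probability that a noncentral t with these parameters exceeds the one-sided 5% critical value.

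**Step 1: reproduce 7.3.** For 10+10 the degrees of freedom are 18, the critical value is 1.734 and the noncentrality is 1.15 × √5 = 2.571. Power is 79.6%, which matches the stated 80%. The effect detectable with exactly 80% power is 1.16, so there is no slack.

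**Step 2: confirm the retention behind 7.2's power.** At 80% recruitment and 80% retention:
- P(at least 20 dyads agree among 29 reached) = 0.951
- P(at least 15 of 20 retained) = 0.804
- Product = 0.765 (0.7646 before rounding), which matches the stated 76%.

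So 7.2 does use 80% retention.

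**Step 3: power when some T2 data are missing.**

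| With T2 data | Split | Power at d = 1.15 | Effect detectable with 80% power |
|---|---|---|---|
| 20 | 10+10 | 79.6% | 1.16 |
| 19 | 10+9 | 77.5% | 1.19 |
| 18 | 9+9 | 75.5% | 1.23 |
| 18 | 10+8 | 75.0% | 1.23 |
| 16 | 8+8 | 70.6% | 1.31 |
| 16 | 9+7 | 70.0% | 1.32 |
| 16 | 10+6 | 68.2% | 1.35 |
| 15 | 8+7 | 67.7% | 1.36 |
| 15 | 9+6 | 66.3% | 1.38 |
| 15 | 10+5 | 63.4% | 1.44 |

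For 8+8 the noncentrality is 1.15 × √4 = 2.300 and the critical value on 14 degrees of freedom is 1.761.

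**Step 4: averages.** The uneven splits are uncommon, so averages describe the loss better than the extremes. If losses fall at random across the 20, the average is 70.1% with exactly 16 retained and 67.2% with exactly 15. If each participant is retained independently, the average over all possible numbers retained is:
- 69.7% at 80% retention
- 72.5% at 85%
- 75.1% at 90%
- 77.4% at 95%

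**Step 5: how often the stated condition would be met.** With independent losses, all 20 are retained with probability 0.80^20 = 0.012 at 80% retention and 0.90^20 = 0.12 at 90%.

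**The case against.** The strongest reply is that the sentence in 7.3 gives its n, effect, alpha, sidedness and test, and that the figure reproduces. That stands: the number is not wrong. What is missing is the condition that n counts participants with T2 data.

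A second reply is that 80% is the lower edge of 7.2's alternative and 15 of 20 is a cut-off, so neither is a forecast. That also stands. Power is higher elsewhere in the alternative, about 75% on average at 90% retention, though still below 80%. A reader might infer that power is at most 71% at 80% retention, but the documents do not support this. The 70.6% is a ceiling only when exactly 16 give T2 data. When true retention is 80%, 17 or more of 20 are retained with probability 0.41, and power is then higher. Nor should the 10+5 figure be taken as typical, since a 10+5 split in either direction has probability of only about 3% when 15 are retained at random.

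A third reply is that intention-to-treat keeps all 20 in the analysis. The sentence says which group a participant is analysed in, whatever intervention was received. It does not supply a T2 value that was never collected, so it does not restore 10 per group.

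Finally, this is an exploratory pilot. Its primary objective is feasibility, and no decision rule uses this t-test. That stands too, and it is why the point is minor.

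**Conclusion.** The point holds as a minor one. The 80% in 7.3 is correct with complete T2 data and is not assured otherwise. At the retention used for 7.2's own power, average power is about 70%, some 10 points below the stated figure. The average shortfall is about 5 points at 90% retention and about 13 points with 15 retained. Put as the chance of missing a true effect of 1.15, it rises from about 20% with complete data to about 30% at 80% retention.

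These figures assume that a retained participant gives T2 data, that loss is unrelated to outcome, and that the t-test uses participants with T2 data.

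A reader might go further and infer that the trial is too small or that the feasibility conclusion is weakened. The documents support neither. The sample size is that of a feasibility pilot, and the feasibility rule does not depend on this power figure. The 0.58 confidence interval width in 7.2 is also outside the point, because it is stated for 10 couples in the PRISMS arm.

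**What to change.** In Section 7.3, replace the unconditional power claim with wording such as: *assuming complete T2 data (10 per group), this gives about 80% power for an effect of 1.15; with 8 per group with T2 data (80% retention), about 71% power, or 80% power for an effect of about 1.31.* Do not describe 80% retention as anticipated, because 7.2 uses it only as a design alternative.

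The cost is one sentence and a less favourable stated power. No further dyads are needed, and the test and the feasibility rule stay as they are.

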2.0 STUDY OBJECTIVES AND ENDPOINTS

The objective of this pilot randomized clinical trial is to test the feasibility of the innovative PRISMS program to enhance personalized supportive care for cancer patients and caregivers during care transition. The aims that will help gather preliminary data for a larger definitive trial are listed below. The indicators of feasibility will include recruitment, enrollment and retention rates as well as automatic recorded online activity comprising navigation time, number of logins, utilization of program sections, which we will collect the data using administration log and study website.

The study outcome, Quality of life (QOL), will be assessed at T1 and T2 using the 27-item Functional Assessment of Chronic Illness Therapy general scale (FACT-G).⁹⁴ We will measure general QOL and physical, social/family, emotional, and functional subdomains.⁹⁵ Caregivers will report QOL using the spouse's version of FACT-G with slightly modified wording.⁹⁶ We will use the PROMIS measures of fatigue, pain, sleep disturbance⁹⁷⁻¹⁰⁰ and Cancer Anxiety¹⁰¹ and Depression¹⁰² to assess patient and caregiver symptom distress at T1 and T2. We will also collect participants' demographics (age, race/ethnicity, income, education) and patient treatment information at T1. At T2, we will collect quantitative data on participant satisfaction of and comfort with using PRISMS.

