2.2 Secondary Objectives

To estimate the magnitude of benefit of PRISMS. We hypothesize that, compared with the patients receiving usual care, the PRISMS users will report (1) greater improvement in their primary outcomes of QOL (overall, physical, emotional, and social QOL); and (2) fewer post-treatment care services related to stoma complications (e.g., ER visits, readmission, use of healthcare providers) from between T1 and T2.

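### For outcomes measured at T1 and T2, section 7.3 names only an unadjusted t-test on change; adjusting the T2 score for T1 would usually be more precise at no data cost.

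*Combined protocol and SAP*

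**What the plan says.** Section 7.3 plans descriptive statistics for quality of life by time point and group, and for health care use by group. Its only between-group method for outcomes measured twice is in the power sentence, which assumes 10 per group, an effect size of 1.15, one-sided 0.05 and 80% power, "using a two-sample t-test to compare the difference in pre-post change (from T1 to T2"). The alternative form applies to outcomes with no T1 value: "or mean level at T2 (if an outcome is only measured at T2"). No baseline-adjusted analysis is named. The only other modelling mentioned is an optional exploratory trajectory analysis of frequently measured patient-reported outcomes.

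On inference, the section says "Unless otherwise specified, all tests will be one-sided at an alpha level 0.05". It refers to confidence intervals only to say that "we will not adjust for multiplicity when computing the CIs in conducting comparisons", giving neither their level nor whether they are one- or two-sided.

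The T1 scores exist. Section 2.0 says that quality of life "will be assessed at T1 and T2 using the 27-item Functional Assessment of Chronic Illness Therapy general scale (FACT-G") and that the PROMIS measures are used "to assess patient and caregiver symptom distress at T1 and T2". The secondary objective in 2.2 is "To estimate the magnitude of benefit of PRISMS", and 2.0 states that "The aims that will help gather preliminary data for a larger definitive trial are listed below".

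**The concern.** A change score is the T2 score minus exactly 1 times the T1 score. That weight is best only when the regression slope of T2 on T1, which is the correlation times SD(T2)/SD(T1), equals 1. When the slope is well below 1, as with a moderate correlation and similar SDs, subtracting the whole T1 score adds noise to the comparison. A model with T1 as a covariate estimates the weight instead.

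What is at stake is the precision of the secondary estimate. Section 2.2 asks for a magnitude, and that magnitude is meant to inform a larger trial. With 10 per arm the 95% CI for the difference in change has an expected half-width of about 0.93 SD of change, so a gain in precision that needs no extra data is worth having. The feasibility decision in 7.2 rests on recruitment and retention and does not use this comparison.

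**Working it through.** **Inputs from section 7.3:** n = 10 per group, effect d = 1.15 SD of change, one-sided alpha 0.05, stated power 80%.

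**Inputs assumed, because the documents do not give them:** correlation rho between T1 and T2 of 0.3, 0.5 and 0.7; SD ratio r = SD(T2)/SD(T1) of 0.8, 1.0, 1.2 and 1.4; bivariate normal scores.

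**1. Reproduce the plan's figure.** Noncentrality = 1.15/√(1/10 + 1/10) = 2.571 on 18 df. One-sided 0.05 power from the noncentral t is 0.796, which agrees with 80%. With 8 per arm (80% retention, the alternative in 7.2) it is 0.706.

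**2. Change-score interval.** The t quantile is 2.101 and √(2/10) = 0.447. Their product is 0.940 SD. Allowing for the expected value of the sample SD, the half-width is 0.93 SD of change.

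**3. Compare the variances.** In units of SD(T1)²:
- change score: 1 + r² − 2·rho·r
- adjusted model residual: r²(1 − rho²)
- difference: (1 − rho·r)², which is never negative.

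In large samples adjustment therefore cannot lose. In small samples, estimating the slope multiplies the expected variance by (N − 3)/(N − 4), where N is the total number analysed: 17/16 = 1.0625 at N = 20 and 13/12 = 1.0833 at N = 16.

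Expected variance ratio (adjusted/change) = [r²(1 − rho²)/(1 + r² − 2·rho·r)] × (N − 3)/(N − 4).

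Example, r = 1, rho = 0.5, N = 20: (0.75/1.00) × 1.0625 = 0.80.

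**4. Results, 10 per arm, true effect held at 1.15 SD of change.** Adjusted power is the one-sided noncentral-t power on 17 df, averaged over chance baseline imbalance. The change-score test has power 0.80 throughout.

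| SD ratio | Variance ratio at rho 0.3 / 0.5 / 0.7 | Adjusted power |
|---|---|---|
| 0.8 | 0.53 / 0.61 / 0.67 | 0.96 / 0.94 / 0.91 |
| 1.0 | 0.69 / 0.80 / 0.90 | 0.91 / 0.87 / 0.83 |
| 1.2 | 0.81 / 0.93 / 1.03 | 0.86 / 0.82 / 0.79 |
| 1.4 | 0.89 / 1.00 / 1.06 | 0.83 / 0.80 / 0.77 |

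With equal SDs the 95% CI half-width falls from 0.93 to 0.77, 0.83 and 0.88 SD of change.

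**5. Where adjustment stops paying.** With equal SDs the ratio is ((1 + rho)/2) × 1.0625, which reaches 1 at rho = 2/1.0625 − 1 = 0.88. At SD ratio 1.2 the model loses for rho between about 0.64 and 0.93, and at 1.4 between about 0.50 and 0.85. The worst case is rho·r = 1, where the loss is 6% in expected variance and power is 0.77.

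**6. With 8 per arm and equal SDs,** adjusted power is 0.83, 0.78 and 0.74 against 0.71. Break-even rho is 2/1.0833 − 1 = 0.85, and the largest expected variance loss is 8%.

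**The case against.** The strongest reply is that nothing here is wrong. The change t-test is valid, its power is correctly stated, and the study is described as exploratory. The test is named only to justify the sample size, while the analyses 7.3 commits to are descriptive. The hypothesis in 2.2 is about improvement, which a change score expresses directly. The gain also depends on two unknown quantities. T1 falls soon after surgery and T2 three months later, so equal SDs cannot be presumed, and the grid above includes ties and small losses.

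Much of this stands, and it is why the point is optional. It does not remove the point:
- If the t-test is only a basis for power, the plan names no between-group estimator for the objective in 2.2, and the same wording fills that gap. Permission for exploratory analyses is not a commitment to adjust.
- The adjusted arm effect is identical whether T2 or change is the response, so the model still answers the question about improvement.
- The trade is uneven: over the range shown, the variance falls by up to 47%, against a worst loss of 6%.

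Two further objections concern the remedy. A two-sided 95% CI can include zero when a one-sided 0.05 test rejects. That is acceptable when the aim is estimation, provided the report says which is which. The power statement also covers outcomes measured only at T2, so its label should too.

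**Conclusion.** The concern holds as an efficiency point of low severity; it is not an error of validity. For outcomes measured at T1 and T2, the only between-group method named leaves the collected T1 score out as a covariate. With 10 per arm, and within the assumed ranges, the expected variance under adjustment runs from 0.53 to 1.06 of the change-score variance. At equal SDs it is 0.69 to 0.90, and power is 0.83 to 0.91 instead of 0.80.

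The size of the gain cannot be fixed from the documents. It rests on assumed correlations, assumed SD ratios and approximate normality. It also supposes that T1 scores are not affected by knowledge of allocation; the documents do not say when randomisation occurs relative to T1. If they were affected, the change score would be affected too, so this does not favour the current test.

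**What to change.** Add to section 7.3, before any outcome data are seen:

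> For each continuous outcome measured at T1 and T2, separately for patients and caregivers, the between-group difference will be estimated from a linear model of the T2 score on arm and T1 score and reported with a two-sided 95% CI. Continuous outcomes measured only at T2 will be compared by a two-sample t-test.

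Keep the statement of 80% power at an effect size of 1.15, labelled as based on the unadjusted two-sample t-test with 10 per group (on change, or on the T2 level where there is no T1 score). State that the CI is for estimation and that any one-sided test is reported separately. The T2-only sentence is limited to continuous outcomes; health care use can stay with the descriptive summaries already planned.

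The cost is wording, with no new data and no change to the sample size. The model spends one degree of freedom. If the slope of T2 on T1 is near 1, the expected variance loss is at most about 6% with 10 per arm or 8% with 8 per arm.

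### The plan promises to analyse all randomised participants, but its only named between-arm test needs a T2 score and no rule covers missing T2, so the secondary comparison is a completer analysis

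*Combined protocol and SAP*

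**What the plan says.** Section 7.3 (Data Analysis Plans) applies intention-to-treat to all analyses, "in which all randomized participants will be analyzed according to their assigned group", and adds "regardless of the extent of intervention actually received". That qualifier deals with how much of PRISMS a person used. It does not mention outcomes that were never measured.

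The same section names one between-arm method, inside its power statement: a "two-sample t-test to compare the difference in pre-post change (from T1 to T2"). Outcomes with no T1 value are instead compared on their T2 means. The power claim reads "This sample size (10 in each group) will ensure 80% power", and it rests on an assumed difference of 1.15 SD with one-sided alpha 0.05.

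Section 2.0 says that QOL "will be assessed at T1 and T2 using the 27-item Functional Assessment of Chronic Illness Therapy general scale (FACT-G"), and it places the PROMIS symptom measures at the same two times. Section 4.3 describes T2 as a telephone assessment about 3 months after baseline. Section 4.5 allows withdrawal at any time. Section 7.2 sets 80% retention or more as the alternative hypothesis and accepts at least 15 of 20 retained as feasible.

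No section gives an imputation rule, a model for incomplete data, a sensitivity analysis, or a statement on seeking T2 after someone stops using PRISMS.

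**The concern.** A change score cannot be computed without T2, and nothing in the plan supplies one. Once anyone lacks T2, the promised analysis set and the named test cannot both hold. The plan's own feasibility rule tolerates that situation, and the power statement uses all 20 dyads with no allowance for loss.

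The comparison is secondary, but it has a use. Section 2.2 sets out to estimate the size of the benefit, and section 1.1 makes a definitive trial conditional on PRISMS looking feasible and beneficial. Section 7.4.2 even describes change in QOL as the primary outcome. An estimate from completers, reported as intention-to-treat, would be carried into that decision with more authority than it has.

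There are plausible reasons for loss to be informative. Section 1.2 links complications after ostomy surgery to reduced QOL and to readmission, and section 4.3 asks PRISMS users for daily synchronisation and frequent early use. These are reasons to plan for the problem, not evidence that it will occur.

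**Working it through.** **Inputs.** From section 7.3: 10 per arm, effect size d = 1.15 SD, one-sided alpha 0.05, power 80%. From section 7.2: at least 15 of 20 retained counts as feasible, and 80% retention is the alternative. Assumption: a participant who is not retained has no T2.

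**1. The plan's own figure.** For a two-sample t-test the noncentrality is d / sqrt(1/n1 + 1/n2), with n1 + n2 − 2 degrees of freedom. With 10 per arm this is 1.15 / sqrt(0.2) = 1.15 / 0.447 = 2.57 on 18 df. The exact noncentral-t power is **79.6%**, which reproduces the stated 80% with T2 present for all 20.

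**2. The same test with T2 missing.**

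| With T2 (arm + arm) | SE of difference (SD) | Power at d = 1.15 | Effect detectable at 80% power |
|---|---|---|---|
| 10 + 10 | 0.447 | 79.6% | 1.16 |
| 8 + 8 (80% retained) | 0.500 | 70.6% | 1.31 |
| 7 + 8 (15 retained) | 0.518 | 67.7% | 1.36 |
| 10 + 5 (15 retained, all loss in one arm) | 0.548 | 63.4% | 1.44 |

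The last row is extreme. If loss is unrelated to arm, the chance that all five losses fall in PRISMS is C(10,5)/C(20,5) = 1.6%.

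**3. How large bias could be (assumptions only).** Suppose those lost would have changed by δ SD less than completers. The between-arm bias is then δ × (k_PRISMS/10 − k_usual/10), where k is the number lost in each arm.
- Two lost in each arm: δ × (0.2 − 0.2) = 0.
- Two lost in PRISMS only, δ = 1: 0.2 SD.
- Five lost in PRISMS only, δ = 1: 0.5 SD, a little below the SE of 0.548 for that split.

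A harsher illustration has no true effect and normal change scores. PRISMS loses its k lowest changers and usual care loses nobody. For k = 1, 2, 3 the simulated bias is 0.17, 0.32 and 0.46 SD, and the one-sided 5% test rejects in about 11%, 18% and 26% of trials. If T2 is missing completely at random, the bias is zero and only power is lost.

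**4. What adjusting for T1 buys.** Assume equal SDs at T1 and T2 and a correlation of 0.5.
- Precision: the SD of change is sqrt(2 × (1 − 0.5)) = 1, so the SE with 10 per arm is 0.447. The residual SD after T1 adjustment is sqrt(1 − 0.25) = 0.866, giving 0.866 × 0.447 = 0.387, or about 0.40 in simulation once the slope is estimated. The change t-test gives 0.45.
- Loss that depends only on T1 and arm: if PRISMS loses its three lowest T1 scorers, the T1 mean of its completers rises by 0.46 SD. The change t-test is then off by (1 − 0.5) × 0.46 = 0.23 SD, here against PRISMS. The T1-adjusted estimate is unbiased.
- Loss that depends on T2 given T1: if those lost have T2 lower by 1 SD at the same T1, the bias is about 0.2 SD (two lost in PRISMS) or 0.5 SD (five lost) for both methods.

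**5. What adjusting does not buy.** With only T1 and T2, a baseline-constrained repeated-measures model has a likelihood that splits into T1 and T2-given-T1. The arm effect appears only in the second part, to which people without T2 contribute nothing. Its arm estimate is that of ANCOVA among those with T2.

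**The case against.** The strongest reply is that the conflict is thin. The plan never says that it will drop anyone; it is silent. The t-test appears only in a power sentence, after a promise of descriptive statistics. The intention-to-treat sentence can be read as being about allocation and adherence, and a person may stop using PRISMS and still answer the T2 call. The study is exploratory, its primary objective is feasibility, and the retention rule counts losses directly. With about 10 per arm, imprecision dominates whatever the model.

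Much of this stands. Completer analysis is the default consequence of the named method, not a declared policy. The primary rule is untouched. However, no other between-arm method is named, and the sentence about all randomised participants is explicit.

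Three stronger readings are tempting and should be resisted.
- A reader might infer that the QOL comparison will be biased in favour of PRISMS. The documents give no loss by arm and no link between loss and change. Completers who are merely healthier in level do not bias a change score; their change must differ, and by different amounts in the two arms.
- A reader might take section 7.2 to forecast 20% loss. It sets 80% retention as an alternative hypothesis and predicts nothing.
- A reader might suppose that a repeated-measures model would restore the intention-to-treat claim by keeping everyone with T1. Step 5 of the working shows that it would not.

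**Conclusion.** The point holds as a mismatch between the stated analysis set and the stated method, together with a power figure that assumes complete follow-up. Under the retention that the plan itself calls feasible, up to 5 of 20 may lack T2. Power for d = 1.15 then falls from 79.6% to between 63.4% and 67.7% for the splits shown, and it is 70.6% with 8 per arm. These figures rest on the plan's own effect size and alpha, and on non-retention meaning no T2.

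Bias is possible but not demonstrated. It is zero if T2 is missing completely at random. It reaches a few tenths of an SD only if loss is related to change and concentrated in one arm. The correlation of 0.5 and the shifts of up to 1 SD are assumptions, since the documents give no values. The consequence is confined to the secondary QOL and symptom comparison, but that comparison informs the definitive trial, so the plan should be corrected.

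**What to change.** 1. In section 7.3, replace the t-test on change with a T1-adjusted comparison of T2 (ANCOVA, or the equivalent baseline-constrained model) for outcomes measured at both times. Do not claim that it recovers participants who lack T2. Outcomes measured only at T2 keep the comparison of T2 means.
2. Add one sensitivity analysis that includes all randomised participants: impute missing T2, then shift the imputed values down by 0.5 and 1 SD, in both arms and in the PRISMS arm only. As a guide, with two PRISMS losses the one-arm shifts move the estimate by about 0.1 and 0.2 SD (0.2 × 0.5 and 0.2 × 1). Report T2 completeness by arm, and say whether T2 is sought from people who stop using PRISMS without withdrawing from the study.
3. Label the main comparison 'as randomised, among those with T2', and state that the 80% power assumes complete T2, giving the figures for 8 + 8 and for 15 retained.

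The cost is a few sentences and a few lines of SAS, with no change to sample size or visits. The adjusted analysis uses one degree of freedom and rests on missing-at-random, which is why item 2 is needed. The stated power will look less favourable.
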